3.3 Study treatments and assessments

The duration of this study will be approximately eight to ten months post-vaccination for all subjects.

On Day 0, subjects will receive one intramuscular (IM) injection into the deltoid region of the non-dominant arm (if possible), of their assigned treatment (30 µg/strain of Quadrivalent VLP Influenza Vaccine or placebo) based on randomization.

The volume of injection will be 0.5 mL for both the vaccine and placebo.

A detailed description of procedures and assessments to be conducted during this study is summarized in [Table 1](#) and [Table 2](#) below.

Table 1: Schedule of Study Assessments

Visit Type	Screening/ Vaccination	Post-vaccination Visits/Contacts			End of Surveillance ¹ (± 3)
		Day 1 (+ 1)	Day 8 (- 1/+ 1)	Day 21 (- 2/+ 3)	
Study Day	Day 0				
Visit Number	1	Phone	Phone	2 (Visit or Phone)	Phone
Informed consent	X				
Demographics	X				
Medical history/prior medication	X				
Vaccination history ²	X				
Inclusion/exclusion criteria	X				
Randomization	X				
Vaccine administration	X				
Immediate surveillance (15 minutes)	X				
Provide eDiary instructions to subjects	X				
Serology for HI, MN, and SRH titers	X ³			X ³	
CMI (peripheral blood mononuclear cell [PBMC]assay)	X ³			X ³	
Vital Signs (blood pressure [BP], heart rate [HR], oral temperature [OT])	X				
Height, weight, and body mass index (BMI)	X				
History/symptom-directed physical examination	X				
Urine (dipstick) pregnancy test	X				
Oral digital thermometer and instructions on reactions and respiratory illness symptoms ⁴	X				
Collection of solicited local/ systemic reactions	X	X	X	X	
Concomitant medications	At any time during the study period				
Collection of respiratory illness symptoms through passive and active surveillance	
Passive Surveillance: Subjects will be instructed to contact the study site if they experience symptoms of respiratory illness from Day 14 until the end of the surveillance period¹.
 
Active Surveillance: Between Day 14 and the end of the surveillance period¹, the subjects will be contacted a minimum of three times per week. At least one of these contacts each week will be through a scripted telephone call, with the remaining contacts via text messaging; a higher proportion of telephone contacts may be used if deemed appropriate by the clinic site (e.g. difficulty in obtaining responses via text messaging).
				
Collection of NP swabs for laboratory confirmation of influenza ⁵	From Day 14 until the end of the influenza surveillance period ¹ , NP swabs will be collected from subjects who report a new or a worsening respiratory illness (as defined in the protocol). Swabs will be collected within 36 hours (preferably within 24 hours) after reporting of the qualifying respiratory illness				

	symptoms.
Collection of disease burden and health care information ⁶	For each case of respiratory illness (as defined in the protocol), a questionnaire on disease burden will be completed by telephone at the end of the 30-day follow up period for the illness, regardless of whether or not a swab is obtained. Subjects will be provided with a memory aid to facilitate accurate reporting.
AEs, Serious Adverse Events (SAEs), and NOCDs ⁷	At any time during the study period
Termination record	X

¹ The end of the surveillance period is targeted as approximately 30 April 2018; however, the duration of surveillance period may be adjusted, based on the observed epidemiology during the season in participating countries.

² Information on past influenza vaccinations for 24 months prior to study entry

³ Only a subset of 400 subjects will have a blood draw for CMI and humoral immunogenicity testing. This subset will be comprised of the first subjects enrolled in pre-defined sites in North America; a representative age distribution will be targeted.

⁴ After vaccination, subjects will be instructed on the memory aid and eDiary provided for their use for recording reactions, AEs, concomitant medication use, and respiratory illness symptoms. They will be reminded of the reportable respiratory illness symptoms that will trigger the need for NP swabbing, as well as of the overall active and passive surveillance process.

⁵ Swabs are to be collected from any subject with a respiratory illness from Day 14 to the end of the surveillance period of the study. If the respiratory illness starts prior to Day 14, swabs are not to be collected, even if symptoms persist beyond Day 14.

⁶ A questionnaire for the collection of disease burden (please refer to protocol) and includes occurrences of any of the following in association with any respiratory illness with onset from Day 14 to the end of the surveillance period: pneumonia (clinical diagnosis), new onset or exacerbations of pre-existing cardio-respiratory conditions, hospitalizations, emergency room visits, and non-routine medical office visits, as well as any additional diagnoses associated with the illness.

⁷ Adverse events will be collected up to Day 21; SAEs, AEs leading to withdrawal, and NOCDs will be collected through to the end of the study. Specific contacts for the collection of information regarding all of these events will occur on Day 21 (in the surveillance telephone call on or shortly after Day 21 or during the Day 21 visit [for the subset of subjects participating CMI and humoral immunogenicity testing]) and during the end of surveillance telephone contact for SAEs, AEs leading to withdrawal, and NOCDs.

Table 2 Time and Events Schedule: Respiratory Illness Onset and Follow Up

Days after Reporting of Respiratory Illness	0-1.5 Days	0-1.5 Days ¹	Monitoring ²	30 (+ 7) Days ³
Contact Type	Phone	Visit	Phone / Text Messaging	Phone
Verify information on respiratory illnesses and schedule appointment (at clinic or home) for two NP swabs within 36 hours (preferably within 24 hours) of the reporting of a respiratory illness	X			
Remind subject to continue to record data and in a timely manner	X			
Collection of the two NP swabs ¹		X		
Collection of reportable concomitant medications	X	X	X	X
Collection of information on respiratory illness symptoms ⁴	X	X	X	X
Collection of disease burden and health care information				X

¹ Swabs are to be collected within 36 hours after reporting of the respiratory illness (preferably within 24 hours) and prior to the use of influenza antiviral treatment medication (e.g. oseltamivir, zanamivir, rapivab).

² After NP swab collection and until the final 30 (+ 7) day follow-up, the planned active surveillance (phone and text messaging) will continue and will include questions on the respiratory illness progression.

³ The seven-day window allows provision to complete the telephone call. Information from more than 30 days from respiratory illness onset does not need to be collected.

⁴ During collection of information on respiratory illness symptoms, the presence or absence of concurrent systemic symptoms (i.e. fever, feverishness [feeling of warmth], chills [shivering], tiredness [fatigue], headache, myalgia [muscle aches], nausea, vomiting, or diarrhea) will also be collected.

4 STUDY ENDPOINTS

4.1 Efficacy Endpoints:

4.1.1 Primary efficacy endpoint

- Occurrences of protocol-defined respiratory illness due to laboratory-confirmed influenza (≥ 14 days post-vaccination) caused by influenza viral types/subtypes that are matched (and/or antigenically similar) to the strains covered in the vaccine formulation.

4.1.2 Secondary efficacy endpoints

The secondary efficacy endpoints of this study are:

- Occurrences of protocol-defined respiratory illness due to laboratory-confirmed influenza (≥ 14 days post-vaccination) caused by any influenza viral types/subtypes (matched, mismatched, and un-typed).
- Occurrences of laboratory-confirmed influenza (according to protocol defined ILI) illnesses (≥ 14 days post-vaccination) caused by influenza viral types/subtypes that are matched (and/or antigenically similar) to the strains covered in the vaccine formulation.
- Occurrences of laboratory-confirmed influenza (according to protocol defined ILI) illnesses (≥ 14 days post-vaccination) caused by any influenza viral types/subtypes (matched, mismatched, and un-typed).
- Occurrences of protocol-defined ILI ≥ 14 days post-vaccination (confirmed or not).

4.1.3 Exploratory endpoints

The exploratory endpoints of this study are:

- Occurrences, per age stratum, of laboratory-confirmed influenza (≥ 14 days post-vaccination) caused by influenza viral types/subtypes that are matched (and/or antigenically similar) to the strains covered in the vaccine formulations, according to protocol-defined respiratory illness;
- Occurrences of laboratory-confirmed influenza illnesses (≥ 14 days post-vaccination) caused by mismatched influenza viral strains, according to protocol-defined respiratory illness;
- Occurrences of respiratory illness ≥ 14 days post-vaccination (confirmed or not).

4.2 Safety endpoints

4.2.1 Secondary safety endpoints

The safety endpoints of this study are:

- Percentage, intensity, and relationship to vaccination of immediate complaints (15 minutes post-vaccination);

- Percentage, intensity, and relationship to vaccination of solicited local and systemic signs and symptoms (for seven days following study vaccine administration);
- Percentage, intensity, and relationship of TEAEs for 21 days following study vaccine administration;
- Occurrences of deaths, SAEs, AEs leading to withdrawal, and NOCDs up to the end of the surveillance period.

4.2.2 Exploratory endpoints

- Information on respiratory illness outcome, occurrences of pneumonia, new onset or exacerbations of cardio-respiratory conditions, and health care utilization during the entire trial follow up period. These results will be summarized separately and not be included in the CSR.

4.3 Immunogenicity endpoints (subset of subjects)

4.3.1 Secondary endpoints

- HI antibody response induced by the Quadrivalent VLP Influenza Vaccine against the homologous and heterologous influenza strains on Days 0 and 21 in a subset of 400 subjects (300 who received the VLP vaccine and 100 who received the placebo). HI antibody titers will be analyzed as follows:
 - Geometric Mean Titers (GMT) of HI antibody on Days 0 and 21;
 - Seroconversion (SC) rate: the proportion of subjects in a given treatment group with either a ≥ 4 -fold increase in reciprocal HI titers between Day 0 and Day 21 or a rise of undetectable HI titer (i.e. < 10) pre-vaccination (Day 0) to an HI titer of ≥ 40 on Day 21;
 - Seroprotection (SP) rate: the proportion of subjects in a given treatment group attaining a reciprocal HI titer of ≥ 40 on Day 21 (the percentage of vaccine recipients with a serum HI titer of at least 1:40 following vaccination);
 - Geometric Mean Fold Rise (GMFR): the geometric mean of the ratio of GMTs (Day 21/Day 0).
- MN antibody response induced by the Quadrivalent VLP Influenza Vaccine against the homologous influenza strains on Days 0 and 21, in the subset of 400 subjects, will be analysed as follows:
 - GMTs of MN antibody on Days 0 and 21;
 - SC rate: the proportion of subjects in a given treatment group with either a ≥ 4 -fold increase in reciprocal MN titers between Day 0 and Day 21 or a rise of undetectable MN titer (i.e. < 14.1) pre-vaccination (Day 0) to an MN titer of ≥ 56.4 at Day 21 post-vaccination ;GMFR (Day 21/Day 0).

Note: A number of studies show the MN assay to have a two-fold or higher sensitivity than the HI assay. However, there is still limited data available on the comparative

sensitivities of these two assays and the data that is available and is largely focused on H1N1 and H3N2. As a result, since this is a secondary analysis with a relatively small sample size, a conservative approach was taken by using the HI assay correlates of protection for the MN assay.

- SRH antibody response induced by the Quadrivalent VLP Influenza Vaccine against the homologous strains on Days 0 and 21 in a subset of 400 subjects will be analysed as follows:
 - Geometric Mean Areas (GMA) of SRH antibody on Days 0 and 21;
 - SC rate: proportion of subjects in a given treatment group showing at least 50 % increase in GMA between Days 0 and 21;
 - SP rate: the proportion of subjects in a given treatment group attaining an area $\geq 25 \text{ mm}^2$ following vaccination (Day 21);
 - GMFR: the geometric mean of the ratio of GMAs (Day 21/Day 0).

4.3.2 Exploratory endpoints

- CMI response induced by the Quadrivalent VLP Influenza Vaccine against homologous and heterologous strains on Day 21 (in the subset of 400 subjects).

CMI responses against homologous and heterologous strains will be evaluated by measuring the % response in CD4+ Cells for parameters as below:

1. IFN- γ + IL-2+ TNF- α +
2. IFN- γ - IL-2+ TNF- α +
3. IFN- γ + IL-2- TNF- α +
4. IFN- γ + IL-2+ TNF- α -
5. IFN- γ - IL-2- TNF- α +
6. IFN- γ - IL-2+ TNF- α -
7. IFN- γ + IL-2- TNF- α -
8. SUM of IFN- γ + (the sum of all IFN- γ + responses; i.e. 1+3+4+7, from the list above)
9. SUM of IL-2+ (the sum of all IL-2+ responses; i.e. 1+2+4+6, from the list above)
10. SUM of TNF- α + (the sum of all TNF- α + responses; i.e. 1+2+3+5, from the list above)
11. SUM of total responsive (CD4+ expressing one cytokine; i.e. sum of all elements from the list above).

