8.7.3 Analysis of Exploratory Endpoint

The exploratory immunogenicity endpoint is defined in 4.3.2

The CMI response induced by the Quadrivalent VLP Influenza Vaccine against homologous and heterologous strains on Day 21 (in the subset of 400 subjects) will be compared between the treatment groups using non-parametric (Wilcoxon) models for each strain and parameter by age group and overall.

For CMI response CD4+ cells results will be presented along with available subjects (n), in terms of mean, median, SD, min and max. For the p-value calculation between the treatment groups for individual parameters, Wilcoxon rank-sum test will be used for Day 21, whereas the p-value will be calculated using Wilcoxon signed rank test for the difference between Day 0 and Day 21 values.

In addition, an individual listing will be provided to include CMI CD4+ cells response for each parameter with % response CD4+cells by subject and age stratum. The responses of each parameter will be illustrated using plots such as box plots by treatment group with parameters as X-axis and percentage of CD4+ T cells (%) as Y-axis.

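### SAP 4.3.2, item 11: the rule for total responding CD4+ cells, read literally, adds the overlapping sums 8-10 to subsets 1-7 and counts each cell two to four times

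*SAP*

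**What the plan says.** SAP 4.3.2 measures the CMI response as a percentage of CD4+ cells on eleven parameters. Items 1-7 are the seven positive/negative combinations of IFN-γ, IL-2 and TNF-α with at least one cytokine positive. Item 1 is triple-positive, items 2-4 are double-positive and items 5-7 are single-positive.

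Items 8-10 are sums with their components spelled out:

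- Item 8, IFN-γ: "the sum of all IFN- γ + responses; i.e. 1+3+4+7, from the list above"
- Item 9, IL-2: "the sum of all IL-2+ responses; i.e. 1+2+4+6, from the list above"
- Item 10, TNF-α: "the sum of all TNF- α + responses; i.e. 1+2+3+5, from the list above"

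Item 11 gives no component numbers: "SUM of total responsive (CD4+ expressing one cytokine; i.e. sum of all elements from the list above".

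SAP 8.7.3 has the CMI response "compared between the treatment groups using non-parametric (Wilcoxon) models for each strain and parameter by age group and overall". It adds signed-rank tests of Day 0 against Day 21, descriptive statistics, subject listings, and plots with the percentage of CD4+ T cells on the vertical axis. It does not define item 11 again. Protocol 12.6.2 leaves further CMI detail to the SAP.

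**The concern.** Item 11 is the only aggregate in the list that covers all three cytokines, and SAP 4.3.2 is the only place that defines it. Its formula and its gloss point to different quantities, and neither, read literally, is the number of cells responding with any cytokine. A programmer who follows the formula adds sums 8-10 on top of the subsets they are built from. One who follows the gloss drops every cell that makes two or three cytokines. Either way, a value labelled as a total percentage of CD4+ cells would be summarised, plotted and tested without being that total.

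**Working it through.** **Inputs.** All come from SAP 4.3.2. Write x1 to x7 for the percentages in subsets 1-7. The documents give no subset frequencies, so the percentages used below are assumptions for illustration.

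**Step 1: check the SAP's own sums.** IFN-γ is positive in subsets 1, 3, 4 and 7; IL-2 in 1, 2, 4 and 6; TNF-α in 1, 2, 3 and 5. These match items 8, 9 and 10 exactly, so those formulas are right.

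**Step 2: add items 8-10.** Subset 1 appears in all three sums, subsets 2-4 in two each, and subsets 5-7 in one each:

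8 + 9 + 10 = 3·x1 + 2·(x2+x3+x4) + (x5+x6+x7)

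**Step 3: literal item 11.** Adding items 1-7 once more:

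sum of items 1-10 = 4·x1 + 3·(x2+x3+x4) + 2·(x5+x6+x7)

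The weight of a subset is 1 plus the number of cytokines it expresses.

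**Step 4: size of the inflation.** Let s, d and t be the shares of responding cells that are single-, double- and triple-positive, with s + d + t = 1. The literal sum divided by the true total is 2s + 3d + 4t.

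| Assumed mix s/d/t | Calculation | Ratio to true total |
|---|---|---|
| 100/0/0 % | 2(1) | 2.0 |
| 60/30/10 % | 2(0.6) + 3(0.3) + 4(0.1) | 2.5 |
| 20/30/50 % | 2(0.2) + 3(0.3) + 4(0.5) | 3.3 |
| 0/0/100 % | 4(1) | 4.0 |

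**Step 5: three readings on the same data.** Assume 0.1% in each of the seven subsets.

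| Reading of item 11 | Components | Value |
|---|---|---|
| Label (all responders) | 1 to 7 | 7 × 0.1 = 0.7% |
| Formula, literal | 1 to 10 | 4(0.1) + 3(0.3) + 2(0.3) = 1.9% |
| Gloss, literal (exactly one) | 5 to 7 | 3 × 0.1 = 0.3% |

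The formula gives 1.9/0.7 = 2.71 times the true total, and the gloss gives 0.3/0.7 = 0.43 times.

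**Step 6: effect on the rank tests.** If every sample had the same mix, the ratio in step 4 would be one constant, and both the rank-sum and signed-rank tests would be unchanged. If mixes differ, they need not be. Take two samples with a true total of 0.2%:

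- 0.1% in subset 1 and 0.1% in subset 5: literal value 4(0.1) + 2(0.1) = 0.6%
- 0.2% in subset 5: literal value 2(0.2) = 0.4%

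A tie becomes a difference. Order can also reverse: an all-triple-positive sample with true total a scores 4a, and an all-single-positive sample with true total b scores 2b. The first therefore ranks higher whenever a > b/2, even if a < b.

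**The case against.** The best defence is that the list explains itself. Items 8-10 use the same phrase about the list above, and each names only subsets 1-7. When items 9 and 10 are reached, earlier sum rows already stand above them, and none is an addend. The label speaks of total responders and the unit is a percentage of CD4+ cells, which the ten-line sum would not be. The gloss does not say exactly one or only one, so at least one is a natural sense. Finally, subsets 1-7 are summarised and listed beside item 11, so a miscalculated total could be noticed.

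Most of this stands as evidence of intent: 1+2+3+4+5+6+7 is very probably what was meant. It does not repair the text. Items 8-10 are unambiguous because they give item numbers, and item 11 alone gives none. Its instruction is to add all elements, and sum rows are among them. Being able to spot an error afterwards does not replace a stated rule.

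A reader might also infer that the main CMI readout is at risk. The documents do not support that: no passage gives item 11 priority over the other ten parameters, and SAP 8.7.3 treats them alike.

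**Conclusion.** Item 11 is wrong as literally written, although its intent can be guessed. Followed literally, the formula would overstate the percentage of responding CD4+ cells by a factor between 2 and 4. Those limits follow from the subset structure alone; any figure between them depends on an assumed cytokine mix. Between-group and Day 0 to Day 21 Wilcoxon results could change, but only if that sum is actually programmed and the mix differs between subjects or visits.

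Two stronger readings are tempting and should be resisted. One is that the analysis will be computed wrongly: table shells and programming are kept outside the SAP, and the likely intent is correct. The other is that the vaccine-placebo comparison is distorted in a known direction. Protocol 1.3.2.3 does report a poly-functional CD4+ response to the vaccine in earlier studies, and the literal sum gives such cells extra weight. But with no subset frequencies in the documents, neither the size nor the practical effect can be established.

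The consequence is limited to one exploratory CMI parameter in the 400-subject subset. The primary endpoint, alpha, power and sample size are untouched.

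**What to change.** In SAP 4.3.2, redefine item 11 as: *CD4+ expressing at least one cytokine; i.e. 1+2+3+4+5+6+7*. This matches the way items 8-10 are written and removes both competing readings. Confirm that the separate table, figure and listing templates and the derivation code use the same seven components.

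The cost is one line in the SAP, best made before the CMI outputs are programmed. It needs no new data and no change to the tests.

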5 SAMPLE SIZE AND POWER

The sample size of approximately 10,000 subjects (5,000 subjects per treatment group) was selected based on the assumption that the Quadrivalent VLP Influenza Vaccine would have a VE of at least 70% and that the attack rate in unvaccinated subjects (ARU) would be 2% or greater for laboratory-confirmed influenza cases caused by vaccine-matched strains. The sample size was chosen to have 90% power to determine whether the lower bound (LB) of the two-sided 95% CI for the primary endpoint would be greater than 40%, assuming a 10% attrition rate.

If the ARU is lower than 2%, but greater than or equal to 1.5%, this sample size will have an 80% power to determine whether the LB of the two-sided 95% CI for the primary endpoint (VE) would be greater than 40%, assuming a 10% attrition rate.

A protocol amendment will be issued to address changes to the enrollment plan or to the study extension into another season to enrol more subjects in the event of insufficient ARU.

Table 3 shows the sample size simulations result. The simulation was repeated 1000 times in order to calculate the power.

Table 3 Sample Size Simulation Result

Placebo Control AR (ARU)	VE (vs placebo)	LB of 95% CI	Power	Sample Size per Group
2%	70%	40%	90%	4430
1.50%	70%	40%	80%	4490

[Note] Under the assumptions of 70% vaccine efficacy (VE) and 2% influenza attack rate (Placebo), we expect a total of 116 to 130 cases of influenza (89 cases for Placebo and 27 cases for VLP in case of 4430 per group considering 10% dropout rate, 100 cases for Placebo and 30 cases for 5000 per group).

If the influenza attack rate is lower than 2%, but greater than or equal to 1.5%, we expect a minimum of 89 total cases.

Immunogenicity Subset

A sample size of 300 subjects (for the VLP vaccine group) was selected to ensure that the LBs of the 95% CI for the co-primary endpoints (SC and SP rates) for each strain meet CBER's criteria with 80% power (individual power is 97.4%).

